**Table 11 Serum RSV-Specific Baseline and Individual Peak Geometric Mean Titers – FAS and PPS**

	Analysis group							
	Adult low (N=18 b )		Adult standard (N=18)		Elderly standard (N=18)		Placebo a (N=9)	
Week (Visit)	GMT	95% CI	GMT	95% CI	GMT	95% CI	GMT	95% CI
Serum RSV-specific IgG ELISA GMT								
Week 0 (V1)	1146	915, 1437	1121	830, 1512	913	726, 1149	1005	710, 1422
Individual Peak GMT	1807	1435, 2276	2238	1622, 3089	2286	1725, 3030	1289	913, 1820
Serum RSV-specific PRNT (strain A) GMT								
Week 0 (V1)	546	380, 783	652	474, 897	625	456, 857	524	374, 734
Individual Peak GMT	926	676, 1268	1394	1087, 1788	944	677, 1315	782	560, 1093
Serum RSV-specific PRNT (strain B) GMT								
Week 0 (V1)	256	173, 379	327	190, 561	242	154, 380	231	116, 456
Individual Peak GMT	379	245, 587	512	322, 814	374	231, 604	347	189, 636
CI = confidence interval; ELISA = enzyme-linked immunosorbent assay; FAS = full analysis set; GMT = geometric mean titers; IgG = immunoglobulin G; PPS = per protocol set; RSV = respiratory syncytial virus								
a Adult and elderly placebo combined.								
b Only 17 of 18 subjects had available data in this group at Week 8 (V7).								
Source: MVA-RSV-001 Clinical Study Report (Ed. 1), Tables 15.2.2.5, 15.2.4.5 and 15.2.5.5.								

The cellular immune response was assessed using an IFN- $\gamma$ /IL-4 ELISPOT assay using three different RSV peptide pools (F, G and N) as well as RSV for stimulation. IFN- $\gamma$  secreting T cells specific for the F, G and N protein increased in all active treatment groups, with no substantial differences between vaccine dose and age whereas numbers of IL-4 producing T cells were low or below the detection limit. No dose dependency was seen in terms of Geometric Mean Spot Forming Units (GMSFUs). The T cell response boosted by the normal dose in the adult and elderly group was comparable. The responder rate based on IFN- $\gamma$  producing PBMCs was highest in the elderly standard dose group, ranging from 66.7% (12/18) to 94.4% (17/18) of subjects for all stimulating agents. Responder rates based on IFN- $\gamma$  and IL-4 producing PBMCs are summarized in [Table 12](#).

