### 9.2 Sample Size Calculation

The primary analysis will be performed on the PRNT (A strain) titers 2 weeks after the last vaccination in the main trial. Testing of the primary objective will be performed by assuming that the  $\log_{10}$  of the titers are normally distributed. Testing will be conducted in a descriptive manner and no adjustment for multiple testing will be performed.

The upper 95% confidence limit of the standard deviation (SD) of the  $\log_{10}$  titers from the Phase I trial RSV-MVA-001 at Visit 6 (2 weeks post second vaccination) was calculated as 0.46 (the SD was very similar in all groups).

The GMTs, GMFIs from baseline, and the response rates and associated 95 % confidence limits will be presented for each group at each sampling point.

The following descriptive comparison of the ratios of the GMTs between groups will be calculated along with the corresponding 95% Confidence Interval by assuming that the  $\log_{10}$  PRNT (A strain) titers are normally distributed:

1. Group 2 / Group 1 – Two vaccinations compared to one vaccination using Dose 1
2. Group 4 / Group 3 – Two vaccinations compared to one vaccination using Dose 2
3. Group 3 / Group 1 – Dose 2 compared to Dose 1 using one vaccination
4. Group 4 / Group 2 – Dose 2 compared to Dose 1 using two vaccinations
5. Group 2 / Group 5 – Two vaccinations using Dose 1 compared to Placebo
6. Group 4 / Group 5 – Two vaccinations using Dose 2 compared to Placebo

With a group sample size of 70 per group (recruiting 80 per group to account for 12 % dropouts), and an assumed SD of 0.46 for the  $\log_{10}$  PRNT titers (A strain), this will give 80 % power to detect a relative change in titers from the Group 1 of a 66 % increase. The SD is similar to what was seen in the RSV Phase I trial (RSV-MVA-001).

A secondary descriptive quadratic orthogonal regression of the  $\log_{10}$  titers for the three doses using Group 2, Group 4 and Group 5 will also be performed. If the linear contrast (i.e. slope) of the regression fit is significant at the standard significance level of 0.05 then a dose response relationship will have been demonstrated. If the quadratic contrast is significantly different from zero then this will indicate that the dose response is not linear within the dose range used in this trial. Assuming the quadratic effect is negative over the higher dose ranges, this will be seen as confirmation of a plateau effect in terms of responses for higher dose.

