**Fold Increase**

The fold increase is defined as a subject's post-Baseline titer at Visit X, divided by the baseline titer.

Study specific version: 1.0  
Study specific version Date: 31-May-17

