#### **Primary immunogenicity endpoint: PRNT (A strain) titers**

The primary analysis of the primary endpoint is Geometric Mean Titers (GMTs) after one or two MVA-BN-RSV vaccinations or placebo measured by Plaque Reduction Neutralization Test (PRNT; against strain A) 2 weeks post last vaccination.

The primary immunogenicity endpoint will also be summarized descriptively using the geometric mean of fold increase, positivity rates (including associated 95% CI's), and response rates (including associated 95% CI's) for each treatment group, and by age group at each sampling point.

In addition, the following descriptive comparison of the ratios of the GMTs and GMFI's between treatment groups by visit will be calculated along with the corresponding 95% CI by assuming that the  $\log_{10}$  PRNT (A strain) titers and  $\log_{10}$  PRNT (A strain) Fold Increases are normally distributed:

1. Group 2 / Group 1 – Two vaccinations compared to one vaccination using Dose 1
2. Group 4 / Group 3 – Two vaccinations compared to one vaccination using Dose 2
3. Group 3 / Group 1 – Dose 2 compared to Dose 1 using one vaccination
4. Group 4 / Group 2 – Dose 2 compared to Dose 1 using two vaccinations
5. Group 2 / Group 5 – Two vaccinations using Dose 1 compared to Placebo
6. Group 4 / Group 5 – Two vaccinations using Dose 2 compared to Placebo

As a secondary descriptive analysis for the primary immunogenicity endpoint, an ANOVA model (with dose and age group as independent variables) of the  $\log_{10}$  titers for the three doses

using Group 2, Group 4, and Group 5 will be performed. For Group 5 (2 vaccinations of Placebo), a dose value of 1 will be used to facilitate the log transformation of the dose. The dose response relationship will be explored in this analysis using linear and quadratic orthogonal contrasts. If the linear contrast (i.e. slope) of the regression fit is significant at the standard significance level of 0.05 then a dose response relationship will have been demonstrated. If the quadratic contrast is significantly different from zero then this will indicate that the dose response is not linear within the dose range used in this trial. Assuming the quadratic effect is negative over the higher dose ranges, then this will be seen as confirmation of a plateau effect in terms of responses for higher dose. This dose response ANOVA will be performed a second time without age group in the model.

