As an exploratory analysis, an ANOVA will be conducted on the  $\log_{10}$  titers using dose (2 levels), the number of vaccinations (2 levels), and age group (2 levels) as main effects, and dose-by-number of vaccinations as an interaction term. The main effect of dose (2 levels) will not include the placebo treatment group. To further explore whether baseline titers have an effect on dose, a similar ANOVA will be performed where the dependent variable of  $\log_{10}$  titers will be replaced with  $\log_{10}$  Fold Increase.

All ANOVAs will be performed on the FAS only.

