## APPENDIX 1. LIST OF TABLES AND LISTINGS

### LIST OF TABLES

| Number        | Title   |
|---------------|---|
| 14.1   | Disposition and Demographics   |
| 14.1.1        | Eligibility of the Subject and Analysis Sets – All Subjects   |
| 14.1.2        | Overall Assessment: Reason for Withdrawal from 2nd Vaccination/Premature Discontinuation – All Subjects |
| 14.1.3.1      | Demographic Data – FAS  |
| 14.1.3.2      | Demographic Data – PPS  |
| 14.1.3.3      | Demographic Data – IAS  |
| 14.1.4        | Medical History by System Organ Class and Preferred Term – FAS  |
| 14.1.5        | Concomitant Medication by ATC Class – FAS   |
| 14.1.6        | Compliance: Number of Subjects Who Received Vaccinations – FAS  |
|               |   |
| 14.2   | Immunogenicity   |
| 14.2.1 | Serum RSV-specific PRNT Strain A   |
| 14.2.1.1      | Serum RSV-specific PRNT Strain A: Geometric Mean Titer – FAS  |
| 14.2.1.2      | Serum RSV-specific PRNT Strain A: Geometric Mean Titer – PPS  |
| 14.2.1.3      | Serum RSV-specific PRNT Strain A: Geometric Mean Titer by Age Group – FAS                               |
| 14.2.1.4      | Serum RSV-specific PRNT Strain A: Geometric Mean Titer by Age Group – PPS                               |
| 14.2.1.5      | Serum RSV-specific PRNT Strain A: Fold Increase – FAS   |
| 14.2.1.6      | Serum RSV-specific PRNT Strain A: Fold Increase – PPS   |
| 14.2.1.7      | Serum RSV-specific PRNT Strain A: Fold Increase by Age Group – FAS                                      |
| 14.2.1.8      | Serum RSV-specific PRNT Strain A: Fold Increase by Age Group – PPS                                      |
| 14.2.1.9      | Serum RSV-specific PRNT Strain A: Positivity Rates – FAS  |
| 14.2.1.10     | Serum RSV-specific PRNT Strain A: Positivity Rates – PPS  |
| 14.2.1.11     | Serum RSV-specific PRNT Strain A: Response Rates – FAS  |
| 14.2.1.12     | Serum RSV-specific PRNT Strain A: Response Rates – PPS  |
| 14.2.1.13     | Serum RSV-specific PRNT Strain A: Group Geometric Mean Titer Ratios – FAS                               |
| 14.2.1.14     | Serum RSV-specific PRNT Strain A: Group Geometric Mean Titer Ratios – PPS                               |
| 14.2.1.15     | Serum RSV-specific PRNT Strain A: Group Geometric Mean Fold Increase Ratios – FAS                       |
| 14.2.1.16     | Serum RSV-specific PRNT Strain A: Group Geometric Mean Fold Increase Ratios – PPS                       |

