## 4 Statistical Methods

### 4.1 Planned Sample Size

From two treatment groups selected based on immunogenicity/safety parameters following primary vaccination, approximately 43 subjects will be recruited into the booster sub-study (86 subjects in total). Out of these 86 subjects, approximately 26 subjects (13 subjects for each dose group) will be recruited from the PBMC subgroup.

Based on the variability observed in the  $\log_{10}$  titers for PRNT (A strain) 2 weeks after the second vaccination in the main study, the standard deviation (SD) is estimated to be 0.335 for the  $\log_{10}$  titers 2 weeks after the booster vaccination. A total of 40 evaluable subjects per group will provide 80% power to detect a difference of 0.213 ( $\log_{10}$ -scale) at a significance level of 5% (two-sided), which corresponds to a ratio of 1.63 in GMTs. Considering a drop-out rate of 5%, 43 subjects per group will be enrolled to receive a booster vaccination.

The sample size for the main study has been initially estimated based on the need to detect a significant difference between the two doses to select the optimal dose for further development. However, only a descriptive comparison is planned between the two dose groups in the sub-study.

The primary objective of the booster sub-study is to demonstrate that the immune response of subjects previously vaccinated with MVA-BN-RSV vaccine can be boosted one year later with a single MVA-BN-RSV vaccination. When the sample size is 40, a paired t-test with a 0.025 one-sided significance level will have >80% power to reject the null hypothesis that the difference in immune response ( $\log_{10}$  titers) after the initial vaccination and that after the booster vaccination is 0.08 or farther from zero when the expected difference is 0, assuming that the standard deviation of the differences is 0.168 ( $\log_{10}$ -scale). This comparison is also considered descriptive.

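### The six PRNT strain A group ratios are valid but use neither the Visit 1 titer as a covariate nor the age and site strata; an ANCOVA on data already collected would usually sharpen them (low priority)

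*Protocol*

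**What the plan says.** Protocol 9.2 sets out the main-trial comparison: "The following descriptive comparison of the ratios of the GMTs between groups will be calculated along with the corresponding 95% Confidence Interval". The contrasts are Groups 2/1, 4/3, 3/1, 4/2, 2/5 and 4/5. The only modelling assumption is normality of the log10 titers. Power rests on an SD of 0.46 and 70 evaluable subjects per group, and the testing is called descriptive.

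Main SAP 3.5.7 (31 May 2017) names GMTs as the primary analysis of the primary endpoint. It then lists the same six contrasts for GMTs and GMFIs alike, "between treatment groups by visit will be calculated along with the corresponding 95% CI", with no covariate for either. The fold increase is a subject's "post-Baseline titer at Visit X, divided by the baseline titer". Appendix 1 gives the second set its own tables, titled "Serum RSV-specific PRNT Strain A: Group Geometric Mean Fold Increase Ratios".

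Age group enters the secondary dose-response ANOVA (also run without it), the exploratory dose-by-number ANOVA and the by-age tables (main SAP 3.5.7, 3.6, Appendix 1). Baseline is explored by changing the outcome to log10 fold increase: "To further explore whether baseline titers have an effect on dose, a similar ANOVA will be performed". No listed model has Visit 1 titer as a covariate, and none includes site. Main SAP 1.1 nevertheless stratifies open-phase randomisation by age and site, and the serum draw at Visit 1 is mandatory (Protocol 1.6).

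**The concern.** The six ratios are the between-group evidence for the primary objective, the choice of dose and schedule. Protocol 2.1 describes adults as already exposed to RSV several times, so the Visit 1 titer plausibly predicts the Visit 4 titer. The two planned sets take fixed positions on that relation: the GMT ratio assumes a baseline slope of 0 and the GMFI ratio a slope of 1. Which is more precise depends on a correlation that the plan does not state. Chance imbalance at Visit 1 also moves the two sets apart, and the SAP does not say which one decides. At stake are wider intervals than the data require, and a possible choice between two answers after the results are known.

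**Working it through.** **1. The plan's own figure.** Inputs from Protocol 9.2: n = 70 per group, SD = 0.46, ratio 1.66. The main calculation gives no alpha. Two-sided 0.05, as in the booster calculation, is used.
- Effect: log10(1.66) = 0.220. Standard error: 0.46 × √(2/70) = 0.0778.
- Power: 0.808 by the normal approximation, 0.803 by the noncentral t.
- Detectable ratio at 80% power: 10^(2.80 × 0.0778) = 1.65 (normal) or 1.66 (t). The stated 66% reproduces as an unadjusted two-sample comparison.

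**2. Precision of the three estimators.** Let r be the Visit 1 to Visit 4 correlation of log10 titer. It is assumed here, because the documents do not give it. With equal SDs and a common slope, the CI half-width on the log scale, relative to the GMT ratio, is:
- GMT ratio: 1
- GMFI ratio: √(2(1 − r))
- ANCOVA: √(1 − r²)

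| Assumed r | GMFI | ANCOVA | ANCOVA narrower than GMT ratio | ANCOVA narrower than better planned ratio |
|---|---|---|---|---|
| 0.3 | 1.183 | 0.954 | 5% | 5% (GMT better) |
| 0.5 | 1.000 | 0.866 | 13% | 13% (tie) |
| 0.7 | 0.775 | 0.714 | 29% | 8% (GMFI better) |

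Detectable ratio at 80% power, SD 0.46, 70 per group, as GMT / GMFI / ANCOVA: r = 0.3, 1.65 / 1.81 / 1.61; r = 0.5, 1.65 / 1.65 / 1.54; r = 0.7, 1.65 / 1.47 / 1.43.

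**3. Unequal SDs.** Protocol Table 11 ("Serum RSV-specific PRNT (strain A) GMT") gives for the elderly group (50–65 years, n = 18) SDs of about 0.276 at baseline and 0.290 at peak, back-calculated from the t-based CIs. With q = 0.276/0.290 the GMFI factor is √(1 + q² − 2rq). The gain over the better planned ratio is then 5%, 11% and 6% at r = 0.3, 0.5 and 0.7. These are peak titers, not 2-week titers.

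**4. Cost of useless covariates.** This was simulated with five groups of 70, SD 0.46, one Visit 1 slope, and 16 sites (the protocol's maximum) and age having no effect. Mean half-widths for GMT / GMFI / ANCOVA:
- r = 0: 0.154 / 0.217 / 0.157, so ANCOVA is about 2% wider than the GMT ratio.
- r = 0.3: 0.153 / 0.182 / 0.150, net gain 2%.
- r = 0.5: 0.153 / 0.154 / 0.136, net gain 11%.
- r = 0.7: 0.154 / 0.119 / 0.112, net gain 6%.

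**5. One pooled slope or several.** Simulated variance relative to the GMT ratio, 70 per group:
- Slope 0.7 in every group: GMFI 0.57–0.60, pooled-slope ANCOVA 0.50–0.52. Adding group-by-Visit-1 terms changes this little (0.50–0.52).
- Slopes 0.6 in active groups and 0.95 in placebo: pooled-slope ANCOVA beats the GMFI ratio in all six contrasts.
- Slopes 0.95 in Groups 1 and 2 and 0.3 elsewhere: for Group 2/Group 1, GMFI 0.329, pooled-slope ANCOVA 0.465, ANCOVA with group-by-Visit-1 terms 0.351. The remaining shortfall disappears in large samples.

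**6. How far the two planned ratios can differ.** The GMT ratio divided by the GMFI ratio equals the ratio of the Visit 1 GMTs. With baseline SD 0.276 and 70 per group, chance alone gives a median factor of 10^(0.6745 × 0.276 × √(2/70)) = 1.08, and a 95% limit of 10^(1.96 × 0.276 × √(2/70)) = 1.23.

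**7. Staggered subjects.** The FAS keeps the 12 staggered subjects: 6 each in Groups 2 and 4, from one site, all under 70 (main SAP 1.1). If they differ by an assumed 0.1 to 0.3 log10, with 89 in Group 2 (booster SAP Table 2), the bias factor is 10^(6/89 × 0.1) = 1.02 to 10^(6/89 × 0.3) = 1.05. This affects 2/1, 4/3, 2/5 and 4/5.

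**The case against.** The strongest reply is that nothing here is wrong. The ratios are valid, descriptive and correctly powered, and no decision rule depends on the width of a CI. Age and baseline already receive attention in the ANOVAs, the by-age tables and the GMFI ratios. There is no evidence that site predicts titer. The gain over what is already planned is modest and rests on an unknown r. All of this stands, and it is why the point has low priority. None of it makes the adjusted analysis a worse choice.

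Three stronger readings are tempting, and the documents do not support them.
- *The plan has no leading analysis.* Both documents put the primary analysis on titers, the sample size rests on them, and the protocol lists only GMT ratios. What is missing is narrower: the SAP sets the GMFI ratios beside the GMT ratios without ranking them.
- *The GMT ratio's CI is about twice as wide as it need be.* Booster SAP 4.1 says "the standard deviation (SD) is estimated to be 0.335" and, for paired data, "assuming that the standard deviation of the differences is 0.168". Together they imply r = 1 − 0.168²/(2 × 0.335²) = 0.87. That is a planning assumption for titers after the initial and after the booster vaccination. No source is given, and 0.168 is about half of 0.335. It is not evidence about Visits 1 and 4.
- *ANCOVA always wins.* A single pooled slope does not guarantee this for every contrast (working, step 5).

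The Phase I groups aged 18–49 would suggest larger gains, but this trial enrols from age 55, so they are not used.

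**Conclusion.** The point holds as a nearly free improvement, not as an error. Age group is already modelled elsewhere. What would be new is Visit 1 as a covariate, site, and the use of the model for the six contrasts. In large samples the ANCOVA is at least as precise as either planned ratio, provided that the Visit 1 slopes are common or group-by-Visit-1 terms are fitted. The sizes in the working rest on assumed correlations of 0.3 to 0.7 and, in the main table, on equal SDs. Against the GMT ratio alone the gain can reach 29%. Against the better planned ratio it is at most 13% in that table. The SAP Addendum of 11 October 2017, cited in the booster SAP Introduction, was not available and may bear on this.

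**What to change.** Estimate the six Visit 4 ratios and their 95% CIs from one ANCOVA of log10 PRNT A titer on group, log10 Visit 1 titer, age stratum and site. Include centred group-by-Visit-1 terms, or fit a common slope and add these terms as a sensitivity analysis. Fix a rule for pooling small sites in advance, for example those with fewer than 15 randomised subjects. Name this the leading ratio estimate, and keep the unadjusted GMT and GMFI ratios as descriptive output. Optionally, repeat 2/1, 4/3, 2/5 and 4/5 without the 12 staggered subjects.

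Before unblinding the cost is SAP wording and model code, with no new data. Subjects without a Visit 1 titer drop out, as they already do from the GMFI ratios, and about 2% of CI width is lost if the covariates predict nothing. Booster SAP 2.2.2 says that the main study has been unblinded, so an analysis added from that point must be labelled post hoc.

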### **9.2.1 Treatment Groups/Datasets to be Evaluated**

Analysis of immunogenicity variables will be done on a valid case basis, i.e. for missing observations no imputation technique such as “Last observation carried forward” will be applied, since this could introduce an optimistic bias into the analysis.

#### Full Analysis Set (FAS):

This is the subset of subjects from the main trial who received at least one vaccination and for whom any data are available.

The main analysis of safety as well as humoral and mucosal immunogenicity endpoints of the main trial will be performed on this analysis set.

#### Per Protocol Set (PPS):

This is the subset of subjects in the FAS who have received all vaccinations in the main trial, completed all visits of the active trial phase (Visit 1 to EAP) and adhered to all protocol conditions. Subjects with only minor (not relevant) protocol deviations are included into this dataset.

The decision whether a protocol deviation is major or not for the classification of subjects into the various datasets will be made on a case-by-case basis in a data review meeting (DRM) prior to database lock.

The statistical procedures applied to the FAS for humoral and mucosal immunogenicity endpoints will also be applied to the PPS.

#### Immunogenicity Analysis Set (IAS):

This is the subset of subjects in the FAS which were assigned to the PBMC subgroup.

The main analysis of the cellular immunogenicity endpoints of the main trial will be performed on the IAS.

#### Booster Full Analysis Set (BFAS):

This is the subset of subjects who received a booster vaccination and for whom any post-booster data are available.

The analysis of safety as well as humoral and mucosal immunogenicity endpoints of the booster trial will be performed on this analysis set.

#### Booster Immunogenicity Analysis Set (BIAS):

This is the subset of subjects in the BFAS which were assigned to the PBMC subgroup.

The analysis of the cellular immunogenicity endpoints of the booster trial will be performed on the BIAS.

Additional analysis sets may need to be defined during the data review meeting and would be described in the clinical study report.

## 9.3 Biometrical Evaluation

### 9.3.1 Analysis

As soon as the last subject has completed Visit FU1 and after any necessary settlement of queries etc. in the eCRFs a data review meeting will be held and the subjects will be assigned to the data sets defined for the main trial (FAS, PPS, IAS, see [Section 9.2.1](#)). After the data review meeting and necessary settlement of queries that may arise during the data review meeting, the database will be locked. The safety analysis will then be performed based on this assignment and will include all safety data up to Visit FU1. Results will be reported in the clinical study report.

As soon as the last subject has completed FU2 Visit and after any necessary settlement of queries etc. in the eCRFs a data review meeting will be held. The assignment of the subjects to the datasets as described in [Section 9.2.1](#) will be the same as in the CSR. After the data review meeting and necessary settlement of queries that may arise during the data review meeting, the database will be locked. The final analysis of the main trial will then be performed and will include all immunogenicity results as well as the follow-up safety data. Results of this analysis will be reported in an addendum to the clinical study report.

For the booster substudy, there will be a topline readout when the last subject included in the booster substudy has completed the BFU1 visit, the immunogenicity data up to BFU1 are available, and the data in EDC have been properly cleaned. The set of topline tables and figures will be specified in the statistical analysis plan.

As soon as the last subject included in the booster substudy has completed BFU3 Visit and after any necessary settlement of queries etc. in the eCRFs a data review meeting will be held. Protocol deviations will be reviewed to determine whether an additional analysis set compared to those described in [Section 9.2.1](#) will be needed. After the data review meeting and necessary settlement of queries that may arise during the data review meeting, the database will be locked. The booster substudy analysis will then be performed and will include all immunogenicity results as well as the follow-up safety data. Results of this final analysis will be reported in an addendum to the clinical study report.

